11.7.1.1 Change from Baseline in HbA1c at 26 weeks (Table 5, Analysis 1)

HbA1c values and change from baseline will be summarized by time point and treatment group.

HbA1c will be measured by a central laboratory in a single site in the US which is National Glycohemoglobin Standardization Program (NGSP) Level 1 certified. The estimand of interest on the HbA1c analysis is the difference in change from baseline for HbA1c using the "treatment policy strategy".

For subjects who discontinue from treatment before visit Week 26 or who have no HbA1c measurement at visit Week 26, HbA1c will be assigned to the scheduled time point if they fall within the allowed visit windows (visit Week 26 \pm 4 weeks).

Submissions to Food and Drug Administration (FDA) and European Medicines Agency (EMA) require different methods for efficacy HbA1c evaluation:

For FDA submission, equivalence in change from baseline in HbA1c between Gan & Lee Insulin Glargine Injection (μ_1) and Lantus[®] (μ_2) will be tested using the two one-sided tests (TOST) approach proposed in Schuirmann (1987) (7) with the following null hypothesis:

$$H_0: (\mu_1 - \mu_2) \leq -0.4 \text{ or } (\mu_1 - \mu_2) \geq 0.4$$

Against the alternative hypothesis of:

$$H_1: -0.4 < (\mu_1 - \mu_2) < 0.4$$

with $\alpha=0.05$.

The 90% CI will be estimated using a pattern mixture model that uses multiple imputation (MI) analyzed using Analysis of Covariance (ANCOVA) with treatment included as a fixed effect and baseline HbA1c included as a covariate. Separately in each treatment group, the imputation will use outcomes in subjects who discontinued treatment prior to Week 26 but returned to provide a visit Week 26 HbA1c sample to impute outcomes in subjects without actual visit Week 26 recorded results under the MNAR assumption. No imputation will be performed for missing baseline HbA1c. Equivalence will be assessed based on the 90% CI; no p-values will be computed. Change from baseline in HbA1c between Gan & Lee Insulin glargine Injection and Lantus[®] will be considered equivalent if the 90% CI is within the margins (-0.4%, 0.4%).

For EMA submission, non-inferiority in change from baseline in HbA1c between Gan & Lee Insulin Glargine Injection and Lantus[®] will be tested using the following null hypothesis:

$$H_0: (\mu_1 - \mu_2) \geq 0.4$$

Against the alternative hypothesis of:

$$H_1: (\mu_1 - \mu_2) < 0.4$$

with a 1-sided $\alpha=0.025$.

In addition, the same non-inferiority test with a margin of 0.3% will be performed.

The 95% CI will be estimated using a pattern mixture model that uses multiple imputation analyzed using ANCOVA with treatment included as a fixed effect and baseline HbA1c included as a covariate. Separately in each treatment group, the imputation will use outcomes in subjects who discontinued treatment prior to Week 26 but returned to provide a visit Week 26 HbA1c sample (labeled as the unscheduled) to impute outcomes in subject without actual visit Week 26 recorded results under the MNAR assumption. No imputation will be performed for missing baseline HbA1c.

Analysis of HbA1c will follow a hierarchical testing strategy: first, non-inferiority will be tested using a margin of 0.4%, and only if this test is significant, then non-inferiority will be tested using a margin of 0.3%.

Sponsor: Gan & Lee Pharmaceuticals, USA Corporation
 Protocol no: GL-GLAT2-3002

Statistical Analysis Plan
 Version Date: 16-Nov-2020

Non-inferiority will be assessed based on the 95% CI; no p-values will be computed. Change from baseline in HbA1c between Gan & Lee Glargine Injection and Lantus® will be considered non-inferior if the 95% CI is below the margins of 0.4 and 0.3%, respectively.

For both, FDA and EMA submissions, to estimate the CI of the difference in HbA1c, the pattern-mixture model will be fitted using the SAS® procedure "MIXED" for FAS. A sample SAS code fragment is provided below for reference (note: actual seeds to be used in the analysis are presented below):

```
proc mi data=<data> nimpute=50 seed= 359648 out=<out_data>;
  by trt;
  class unscheduled;
  monotone reg(Week26_HbA1c=base_HbA1c);
  mnar model(Week26_HbA1c / modelobs = (unscheduled = '1'));
  var base_HbA1c;
run;
```

In between these steps, the data will be transposed and then the change from baseline at visit Week 26 will be calculated.

```
proc mixed data=<out_data> out=<lsmeans>;
  by _imputation_;
  class trt;
  model CFB_HbA1c_26 = trt base_HbA1c / ddfm=kr;
run;
proc mianalyze data=<lsmeans>;
  by effect;
  modeleffects estimate;
  stderr;
run;
```

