[figure not shown]
At all visits and phone contacts (except for visits to apply a CGM sensor) the Investigator or designee will review glucose results (especially looking for hypoglycemia), adverse events, changes in concomitant medications, and changes in IP, bolus insulin, and OAM use. At all study visits, the following procedures will be performed: vital signs, body weight, urinalysis, urine pregnancy testing for women of childbearing potential, and an FBG test.

Additional procedures at study visits are as follows: at Weeks 8, 16, and 26, blood for HbA1c will be collected; during the visits at Weeks 12 and 26, subjects will wear their CGM sensors to the site for the site staff to safely remove it, and they will bring their Mealtime & Insulin Dose Record for the site staff to review, and, blood will be collected for routine hematology and chemistry, TSH, free T4, and AIA testing; and at Week 26, a 12-lead ECG and physical examination will be performed. [Figure 1](#) and [Table 1](#) show the study design and study-related procedures, respectively.

If a subject discontinues the study prematurely, site personnel will make a reasonable effort to perform all study activities scheduled for Visit 9 (end of treatment [EOT] visit).

Additionally, it is very important for site personnel to encourage subjects to visit the site at Week 26 ( $\pm 4$  weeks) (and Week 12  $\pm 1$  week if applicable) for a blood sample to be obtained for AIA and HbA1c measurements.

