### 9.11 Early Termination Visit

For any subject who is withdrawn before completing all study visits, the Investigator will ensure that the following steps are taken at an early termination (ET) visit:

- Conduct an ET visit performing study activities listed under Visit 9 ([Section 9.10](#)) no later than 14 days after withdrawal or discontinuation from the study
- If the subject fails to attend a scheduled ET visit, site staff will make at least 2 attempts to contact the subject via telephone and 2 attempts via written communications delivered by courier (delivery should be confirmed and documented). If the subject does not respond to any of these attempts at communication, he or she will be considered lost to follow-up
- Complete all appropriate eCRF pages, providing the date of and explanation for the subject's withdrawal/discontinuation
- When indicated, the Investigator should arrange for appropriate follow-up medical care for the subjects

**If a subject discontinues the study prematurely, it is very important for site personnel to encourage subjects to visit the site at Week 26 ( $\pm 4$  weeks) (and Week 12  $\pm 1$  week, if applicable) for a blood sample to be obtained for A1A and HbA1c measurements.**

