11.7.1.2 Methods for Handling Dropouts and Missing Data

Missing HbA1c data at visit Week 26 will be imputed for the analysis on HbA1c using MI method, performed separately for each treatment group.

Additionally, the robustness of primary analysis results under the MNAR assumption will be explored through multiple sensitivity analysis as listed in Table 5 and detailed in Section 11.7.1.

The pattern of missing data for HbA1c will be provided with a context of Week 26 measurement to be "Completed on schedule", "Returned", or "Not returned". This summary arranges the response data into "patterns" (for example, the number and percentage of subjects with no missing data at baseline and visit week 26).

Sponsor: Gan & Lee Pharmaceuticals, USA Corporation
Protocol no: GL-GLAT2-3002

Statistical Analysis Plan
Version Date: 16-Nov-2020

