- 4) Mixed model repeated measure (MMRM): this sensitivity analysis will include all post-baseline HbA1c measures from each time point as the dependent variable. The independent variables in the model include fixed effects for treatment assignment (2 levels), time (3 post-baseline times), treatment-by-time interaction, and covariate terms for the baseline HbA1c score and baseline HbA1c score-by-time interaction (which allows the effect of baseline covariate parameter to change over time). An unstructured covariance matrix will be used to model the inter-dependencies among the repeated measures. However, if the model does not converge, an alternative covariance matrix will be used which is appropriate for the repeated measurements (e.g., first-order autoregressive). Given the missing data, the Kenward-Roger approximation will be used for calculating the denominator degrees of freedom and adjusting standard errors. If a structured variance-covariance matrix is used, sandwich estimator will be used to estimate the variance of the treatment effect estimate. The FAS will be used to generate the results. (Table 5, Analysis 5)

The SAS code to be used for the repeated measure model is:

```
Proc mixed data=<data>;
  class trt visit subject;
  model HbA1c = trt
        visit
        trt*visit
        base_HbA1c
        base_HbA1c*visit
        / solution ddfm=kr;
  repeated visit / subject = subj type=un;
  lsmeans treatment*visit / pdiff cl;
run;
```

- 5) ERIPD Interaction Analysis for Efficacy – To assess the impact of eligibility related treatment effect on efficacy, this analysis will be a repeat of the main analysis with the addition of the term of presence/absence of ERIPD main effect and an interaction term of treatment*ERIPD. The parameter estimate of the interaction term, 90% CI and p-value will be presented with least square means estimated for each ERIPD group under the treatment arms. (Table 5, Analysis 6)

Additional analysis examining the change from baseline in HbA1c at visit Week 26 in the following subgroups will be presented in a table and a forest plot, by treatment groups but not overall. Missing outcomes were imputed separately in each treatment group using outcomes in subjects who completed the study. These analyses will be conducted according to the FDA submission approach (i.e. 90% CI and 0.4% margin) with MI for the FAS (Table 5, Analysis 7):

- Gender (Male versus Female)
- Age (< 65 versus ≥ 65 years old)

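### The main HbA1c imputation predicts Week 26 from baseline alone and leaves the same subjects' on-study HbA1c unused; one last-value predictor, with a minimum donor count, would be a cheap improvement

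*SAP*

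**What the plan says.** SAP 11.7.1.2 states that "Missing HbA1c data at visit Week 26 will be imputed for the analysis on HbA1c using MI method, performed separately for each treatment group". SAP 11.7.1.1 names the donors: subjects who stopped treatment early but came back for a Week 26 sample. Neither section lists the imputation predictors in words. They appear only in the SAS code, introduced by "A sample SAS code fragment is provided below for reference". That code has "monotone reg(Week26_HbA1c=base_HbA1c" as the regression and "mnar model(Week26_HbA1c / modelobs = (unscheduled = '1" as the restriction to returned discontinuers, run by treatment. Protocol 12.8.1 leaves the details of the imputation to the SAP, so this fragment is the whole specification.

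More HbA1c is collected than the model uses. Protocol 8.1 schedules "at Weeks 8, 16, and 26, blood for" HbA1c. For withdrawn subjects, Protocol 9.11 tells sites to "Conduct an ET visit performing study activities listed under Visit 9", and those activities include HbA1c. Under SAP 11.7.1.1 a value inside Week 26 ± 4 weeks becomes the Week 26 outcome. A value outside that window has no role in the main imputation.

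Two planned analyses in SAP 11.7.1.3 bear on this. For the MMRM, "this sensitivity analysis will include all post-baseline HbA1c measures from each time point as the dependent variable". The tipping-point analysis shifts imputed values in steps of 0.2, in both directions for equivalence, and its imputation code uses treatment and baseline HbA1c only.

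**The concern.** Fitting by arm on returners alone, with baseline as the only predictor, assumes that a non-returner's Week 26 HbA1c is distributed like that of a returner with the same arm and baseline. That assumption is made even where the two subjects' Week 16 or early-termination values plainly differ. Whether a subject comes back may well depend on recent glycaemic control. If it does, and to a different degree in each arm, the imputed values are systematically too low or too high in one arm, and the error passes into the difference that is compared with ±0.4.

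Missing data are not a side issue here. SAP 5.1 allows for no dropouts in the sample size and records more early discontinuation than expected. A second, smaller cost is precision: a good predictor of the missing value is left unused.

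**Working it through.** **Plan's own figures.** The documents give no power, SD or dropout rate for HbA1c, so there is none to reproduce. The stated power concerns the antibody endpoint. For a 30% rate, a 12% margin and 275 per arm, SE = √(2 × 0.3 × 0.7 / 275) = 0.0391, and power = 2Φ(0.12/0.0391 − 1.645) − 1 = 84.6%, against about 85% stated. It does not bear on this point.

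**Inputs from the documents.** 275 per arm; 90% CI against ±0.4; donors and predictor as in the code.

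**Assumed inputs (not in the documents).** SD 1.1; correlation with Week 26 of 0.5 for baseline and 0.6–0.85 for the last on-study value; about 27–44 non-returners and 5–41 returners per arm; selective return at log-odds 1 per SD of recent HbA1c unless stated. Method: Bayesian regression imputation by arm from returners, ANCOVA on baseline, Rubin's rules.

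**Bias, by formula.** Bias ≈ f × (g_test − g_Lantus). Here f is the share of an arm imputed and g is the mean Week 26 HbA1c of returners minus that of non-returners at equal baseline. With 40 of 275 missing, f = 0.145. A bias of 0.04 needs a between-arm gap of 0.04/0.145 = 0.28 points; a bias of 0.09 needs 0.09/0.145 = 0.62 points.

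**Bias, by simulation.** True difference +0.40, 20% dropout (55 per arm), about 22 returners per arm, 600 runs per row. Entries are the mean estimate and the share of runs declaring equivalence.

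| High recent HbA1c lowers return in | Complete data | Baseline only | Baseline + last value |
|---|---|---|---|
| Test arm only | 0.399, 6% | 0.358, 12% | 0.398, 7% |
| Lantus arm only | 0.404, 7% | 0.444, 2% | 0.403, 6% |
| Both arms | 0.390, 7% | 0.389, 6% | 0.392, 6% |
| Neither arm | 0.396, 6% | 0.397, 5% | 0.396, 5% |

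Monte Carlo error on 12% is √(0.12 × 0.88 / 600) = 1.3 points. Against complete data, the baseline-only shift is −0.041, +0.040, −0.001 and +0.001. With f = (55 − 22)/275 = 0.12, the first row implies a gap of 0.041/0.12 = 0.34 points, about 0.3 SD.

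With about 40 non-returners per arm and test-arm selection only, the shift was −0.03 to −0.09 as the log-odds slope went from 0.5 to 1.5. At a true difference of 0.40 and about 25 returners per arm, equivalence was then declared in 12%, 15% and 20% of runs at slopes 0.5, 1.0 and 1.5, against 4–6% with the last value added.

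**Precision, no selective return, 40 non-returners per arm.** SE of the difference:

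| Last-value correlation | Returners per arm | Baseline only | + last value | Change |
|---|---|---|---|---|
| 0.8 | 10 | 0.120 | 0.108 | −10% |
| 0.8 | 15 | 0.107 | 0.097 | −9% |
| 0.8 | 25 | 0.098 | 0.091 | −7% |
| 0.6 | 10 | 0.119 | 0.119 | 0% |
| 0.6 | 15 | 0.106 | 0.103 | −3% |
| 0.6 | 25 | 0.098 | 0.096 | −2% |
| 0.8 | 5 | 0.187 | 0.200 | +7% |
| 0.6 | 5 | 0.185 | 0.260 | +41% |

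Repeat runs put the largest gain at about 12% and the loss at 5 returners as high as about 50%. Entering Weeks 8 and 16 as two separate predictors is worse than one last value: at about 11 returners per arm the 90% half-width went from 0.205 to 0.230–0.236, that is 12–15% wider.

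**The case against.** The case for leaving the model alone has substance.

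- **Direction.** A reader might infer that the model favours equivalence. The documents do not support that. Imputation is by arm, nothing in them suggests that return differs by arm, and the mirror case pushes the other way. This objection stands.
- **Size.** Some selection set-ups give about 0.11, and a reader might take a quarter of the margin (0.10/0.4) as the expected error. That is one corner of an assumed range.
- **Width.** A reader might count a wider CI as a risk of a false claim. In an equivalence test it is conservative, and with very few donors the extra predictor itself widens the CI.
- **Early-termination values.** A reader might say they are ignored altogether. Inside Week 26 ± 4 weeks they are the outcome.
- **Parsimony.** SAP 5.1 says Amendment 3 (25 April 2019) brought in the return procedures, and SAP 10.3 dates the last follow-up to 13 August 2019, 110 days later. Few returners are plausible, and SAP 3.1 makes the returner-donor method, an FDA suggestion, conditional on sufficient data. The last value may also predict poorly once a subject has changed insulin. This stands, and is why a minimum donor count is needed.
- **Existing sensitivity analyses.** The two-way tipping point covers the scenario of test-arm non-returners being worse than imputed, and the MMRM uses every post-baseline value. Both help. But the tipping point says how large a departure would overturn the result, not what departure the on-study values support. The MMRM changes the missing-data assumption and drops the returner pattern, so a discrepancy could not be attributed to the omitted predictor. Neither conditions the returner-based imputation on on-study HbA1c.

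**Conclusion.** The point holds in a limited form. As specified, the main imputation rests on exchangeability of returners and non-returners given arm and baseline, and it leaves out the Week 8, Week 16 and out-of-window early-termination HbA1c.

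If return depends on recent HbA1c differently by arm, the bias is roughly 0.04–0.09 points, or 10–22% of the 0.4 margin. With poorer recent control lowering return and a truly worse test product, the bias is toward equivalence when the selection is in the test arm and away from it when in the Lantus arm. It is about zero when selection is equal. The precision loss is about 2–12% of the SE with 10 or more returners per arm, and close to nil in the least favourable settings; it costs power only.

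All these sizes depend on the assumed SD, correlations, dropout and return pattern, because the documents give none. This is a cheap improvement to the plan, not a flaw that invalidates the main analysis.

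**What to change.** Before database lock:

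1. State the imputation predictors in the text of SAP 11.7.1.1, not only in the code.
2. Add one predictor, `last_HbA1c`: the latest value by date before the Week 26 window, whether from Week 8, Week 16 or early termination, and baseline if there is none. Choosing by date matters, since an early-termination value can follow Week 16.
3. Change the code to `monotone reg(Week26_HbA1c = base_HbA1c last_HbA1c);` and `var base_HbA1c last_HbA1c Week26_HbA1c;`. The present VAR statement omits the imputed variable. Keep the by-arm fit and the returner donors.
4. Use the same model in the main, PPS and PPS3 analyses.
5. Prespecify a minimum number of returners per arm, for example 10, below which the baseline-only model or the all-subjects fallback is used. The SAP spells out that fallback only for the PPS analysis and gives no number; say which applies to the main analysis.
6. Do not enter Weeks 8 and 16 as two separate predictors.

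The cost is SAP wording, one derived variable and one more regression parameter per arm. That parameter can inflate the SE with fewer than about 8–10 returners per arm, which the minimum count controls. For subjects with no later value the two predictors coincide, a simplification to acknowledge in the text.

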11.7.1.2 Methods for Handling Dropouts and Missing Data

Missing HbA1c data at visit Week 26 will be imputed for the analysis on HbA1c using MI method, performed separately for each treatment group.

Additionally, the robustness of primary analysis results under the MNAR assumption will be explored through multiple sensitivity analysis as listed in Table 5 and detailed in Section 11.7.1.

The pattern of missing data for HbA1c will be provided with a context of Week 26 measurement to be "Completed on schedule", "Returned", or "Not returned". This summary arranges the response data into "patterns" (for example, the number and percentage of subjects with no missing data at baseline and visit week 26).

Sponsor: Gan & Lee Pharmaceuticals, USA Corporation
Protocol no: GL-GLAT2-3002

Statistical Analysis Plan
Version Date: 16-Nov-2020

11.7.1.3 Sensitivity Analyses

To evaluate the impact of important protocol deviations and missing data, sensitivity analyses will be performed using the analysis methods described for the FDA equivalence and EMA non-inferiority analyses:

- 1) PPS: Using MI approach as described for main HbA1c analysis. If in the number of subjects who discontinued treatment and return to provide an HbA1c sample at Week 26 is insufficient to perform the MI, the MI will instead be performed using data from all patients with HbA1c results at Week 26 in each treatment group under the assumption of MNAR (Table 5, Analysis 2).
- 2) FAS Completers: This analysis will not use any imputation of missing data. Only subjects with valid baseline and visit Week 26 assessment conducted at actual visit Week 26 and who had treatment until visit Week 26 will be used for the analysis (Table 5, Analysis 3).
- 3) Per Protocol Analysis Set 3 (PPS3) - Subjects with any efficacy-interfering important protocol deviations (EIIPD; as defined in Section 11.3) will be excluded from the analysis. For the subjects in the PPS3, the imputation approach as described for the main analysis will be followed. In the main analysis, subjects with efficacy-interfering important protocol deviations could falsely draw the estimated treatment difference closer. Exclusion of these subjects in this sensitivity analysis will help assess the magnitude, if any, of this effect. (Table 5, Analysis 4)
- 4) Mixed model repeated measure (MMRM): this sensitivity analysis will include all post-baseline HbA1c measures from each time point as the dependent variable. The independent variables in the model include fixed effects for treatment assignment (2 levels), time (3 post-baseline times), treatment-by-time interaction, and covariate terms for the baseline HbA1c score and baseline HbA1c score-by-time interaction (which allows the effect of baseline covariate parameter to change over time). An unstructured covariance matrix will be used to model the inter-dependencies among the repeated measures. However, if the model does not converge, an alternative covariance matrix will be used which is appropriate for the repeated measurements (e.g., first-order autoregressive). Given the missing data, the Kenward-Roger approximation will be used for calculating the denominator degrees of freedom and adjusting standard errors. If a structured variance-covariance matrix is used, sandwich estimator will be used to estimate the variance of the treatment effect estimate. The FAS will be used to generate the results. (Table 5, Analysis 5)

The SAS code to be used for the repeated measure model is:

```
Proc mixed data=<data>;
  class trt visit subject;
  model HbA1c = trt
        visit
        trt*visit
        base_HbA1c
        base_HbA1c*visit
        / solution ddfm=kr;
  repeated visit / subject = subj type=un;
  lsmeans treatment*visit / pdiff cl;
run;
```

- 5) ERIPD Interaction Analysis for Efficacy – To assess the impact of eligibility related treatment effect on efficacy, this analysis will be a repeat of the main analysis with the addition of the term of presence/absence of ERIPD main effect and an interaction term of treatment*ERIPD. The parameter estimate of the interaction term, 90% CI and p-value will be presented with least square means estimated for each ERIPD group under the treatment arms. (Table 5, Analysis 6)

Additional analysis examining the change from baseline in HbA1c at visit Week 26 in the following subgroups will be presented in a table and a forest plot, by treatment groups but not overall. Missing outcomes were imputed separately in each treatment group using outcomes in subjects who completed the study. These analyses will be conducted according to the FDA submission approach (i.e. 90% CI and 0.4% margin) with MI for the FAS (Table 5, Analysis 7):

- Gender (Male versus Female)
- Age (< 65 versus ≥ 65 years old)
- Race (white versus non-white)
- BMI (Obese versus Non-obese)
- Menopausal Status (Pre- versus post-)
- Eligibility Criteria Met (Presence of an eligibility-related important protocol deviation versus no presence of an eligibility-related important protocol deviation). Eligibility-related important protocol deviations are those coded to the Inclusion Criteria or Exclusion Criteria categories (refer to Appendix 4 for details).

Additionally, tipping point analyses with MI approach will be conducted for analyses of change from baseline in HbA1c at visit Week 26 in FAS for both FDA equivalence (2-way tipping point) and EMA non-inferiority submissions. For the MI approach, each missing value will be replaced with a set of plausible values that represent the uncertainty about the right value to impute (Table 5, Analysis 8).

Tipping point analyses evaluate varying combinations of imputed missing data values with added penalties of shift values until the analysis reaches a “tipping point”, or more specifically the point at which the study’s conclusions of equivalence or non-inferiority for HbA1c would change as summarized by the confidence intervals. This sensitivity analysis will explore the effect of the violation of the MAR assumption and will instead examine the results under a MNAR assumption. If the tipping point analysis reveals that the “tipping point” is at an unreasonable shift, then the robustness of the study results under the MAR assumption are supported.

Sponsor: Gan & Lee Pharmaceuticals, USA Corporation
 Protocol no: GL-GLAT2-3002

Statistical Analysis Plan
 Version Date: 16-Nov-2020

A sample SAS code fragment is provided below for reference (note: actual seeds to be used in the analysis are presented below):

```
proc mi data=<data> nimpute=10 seed= 120920 out=<out_data> minimum=. 0 0;
  class trt;
  monotone reg;
  mnar adjust(week_26 /shift = <shift> adjustobs=(trt='Gan & Lee Insulin Glargine Injection'))
        adjust(week_26 /shift = -<shift> adjustobs=(trt='Lantus'))
  var trt base_HbA1c week_26;
run;
```

The following shift values will be used (increase for Gan & Lee Insulin Glargine Injection and decrease for Lantus® simultaneously): 0, 0.2, 0.4, etc. until the conclusion of equivalence or non-inferiority will change, the equivalence 2-way tipping point analysis utilizes a shift in both directions (additionally decrease for Gan & Lee Insulin Glargine Injection and increase for Lantus®). The ANCOVA analyses will be performed as described in Section 11.7.1.1.

